ECMO is well known to cause coagulopathy. High extracorporeal blood flow (BF) along with the large artificial surfaces of ECMO circuit can trigger serial cascades of inflammatory response including coagulation, complement, cytokines and eicosanoid systems with crosstalk among them [4]. The continuous activation of the contact and fibrinolytic systems as well as consumption and dilution of factors occurs within minutes of initiation of ECMO [5]. Platelets adhere to surface fibrinogen and are activated and the resultant platelet aggregation and clumping causes numbers to drop [6]. Correction by platelet transfusion produces only a temporary increase in numbers. Prolonged duration of ECMO exacerbates these

negative effects rendering the critically ill patients at more potential risks of coagulopathy, either bleeding or thrombosis.

Bleeding can rapidly become life-threatening and appears to be out of proportion to the degree of coagulopathy and patient platelet count. Cannulation (7-20%) and surgical site bleeding (6-34%) are common. Intracranial bleeding (1-11%), especially in neonates, gastrointestinal haemorrhage (1-4%), and pulmonary haemorrhage (4-8%) may also occur [7]. Concurrently, extensive thrombosis will not only interfere with the blood flow in the ECMO circuit leading to frequent tube changes, but also cause more devastating systemic complications, such as disseminated intravascular coagulopathy (DIC), cerebrovascular accident, pulmonary embolism, end organ failure, etc. Hemolysis is another well-recognized complication of ECMO with an incidence of between 5% and 8% and can reciprocally aggravate the coagulopathy [8]. The free Hb is monitored as the indicator for screening the microthrombosis in the circuit.

B. Current efforts to decrease the coagulopathy

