To prevent clotting of the cannulae, tubing and particularly of the oxygenator, and, moreover, the serious systemic thromboembolic events, systemic infusion of unfractionated heparin and heparin-bonded circuits are usually needed [6,9]. The thrombus formation is reduced. However, bleeding risk then is increased. The balance between hemostasis and thrombosis is critical. To avoid the adverse effects from commonly-used pharmacological methods, and since blood-surface interaction is a crucial promoter of the subsequent inflammation leading to coagulopathy, it seems more fundamental to treat the major complications by modifying the material of ECMO circuit which now is mainly composed of polyvinylchloride (PVC) compounds. In most patients, the duration of support required is approximately 1 week or longer [10]. The biocompatibility is particularly an important issue regarding the extended period of ECMO use.

1) Systemic Heparinization and Heparin-Bounded Circuit to Prevent Thromboembolic Complications

Serious coagulopathy has been the major complication during ECMO support, either bleeding or thrombosis, leading to high device-related mortality and morbidity. Several efforts have been made on this problem, mainly with the pharmacological interventions. To reduce the thromboembolic

complications, high doses of heparin is usually needed with its major anticoagulant effect by inactivating thrombin and activated factor X (factor Xa) through an antithrombin (AT)-dependent mechanism. However, bleeding risk then increases and attempts should be made to avoid or minimize all non-urgent invasive procedures. Operative interventions in patients on ECMO can be particularly hazardous because of the risk of bleeding and should be avoided if at all possible [11]. Heparin-bounded circuits were developed recently to reduce the use of systemic heparin and have been reported to reduce blood cell trauma [12], complement [13] and granulocyte [14] activation. Nevertheless, systemic heparinization is still advisable because of the risk of end organ damage from microthrombus and fibrin deposition, although the level of heparinization requito red is still under debate. Regular laboratory monitoring with activated partial thromboplastin time (APTT) is required to adjust the doses of heparin accordingly and hence makes resource intensive.

2) Anti-Platelet Agents to Treat Coagulopathy

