Anti-platelet agents such as low-dose aspirin (acetylsalicylic acid) and short-acting GP IIb/IIIa inhibitors like tirofiban and eptifibatide have all been used to treat the thrombosis-bleeding complication by preventing platelets aggregation and possibly reducing inflammation. By using these platelet protecting techniques and adding an aprotinin infusion to block excessive fibrinolysis, one institution has reported a reduction in bleeding complications from 81% to 9% [15]. However, unlike clinical application of APTT to monitor heparin effect, there is no well-established method to guide the optimal use of anti-platelet agents in such a complex system.

C. Improving the biocompatibility of ECMO is a more fundamental approach

Whereas the pharmacological interventions would bring the critical imbalance between hemostasis and thrombosis, efforts to modify the ECMO system may be another essential method to approach the problem. Although ECMO remains a short-term support device, the use of such a circuit for extended periods (days to weeks) has required some modifications, among which the biocompatibility of the material of tubing and circuit system is an important consideration. Biocompatibility is a general term used to describe the suitability of a material for exposure to the body or bodily fluids. It is the ability of a material to perform with an appropriate response in a specific application. Biocompatibility is vital for medical devices. If a material used is not biocompatible, there may be complications such as extended chronic

inflammation at the contact point, generation of materials that are toxic to cells (cytotoxicity), cell disruption, restenosis after treatment, thrombosis, corrosion of an implant, etc. In the setting of ECMO support, using a biocompatible material is thought to minimize the blood-surface interaction, and hence give the control of the inflammatory response from the right beginning to prevent the following activation of serial cascades. Modification of the ECMO circuit with more biocompatible, especially hemocompatible material is reasonably a fundamental way to reduce the potential coagulopathy.

1) Concerns about PVC, the current material of ECMO circuit

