The thickness and dielectric constant of the ZrO_2/Al_2O_3 nanolaminate thin films will be measured using spectroscopic ellipsometry (SE). The structure of ZrO_2/Al_2O_3 nanolaminate thin films will be characterized by transmission electron microscopy (TEM), scanning electron microscopy (SEM), and X-ray photoelectron spectroscopy (XPS). Atomic force microscopy (AFM) will be used for the analysis of surface morphology and roughness.

2) Biological characterization

Basic biological evaluations following ISO 10993/EN 30993 including chemical, mechanical, thermal and aging testing of the ZrO_2/Al_2O_3 nanolaminate thin films are arranged.

3) Hemocompatibility test

Healthy non-smoking volunteers are included to donate fresh bloods via venipuncture for in vitro hemocompatibility test, while those who are pregnant, with bleeding disorders or taking anticoagulants, such as aspirin, NOAC, are excluded. A series of relevant assessments is done as the followings:

a. Serum levels of blood platelet-activating-factors

The blank PVC or PVC with T-ALD/PE-ALD Al_2O_3 films are planned to be immersed in whole blood for 1hr. The bloods are then collected and the sera were separated to determine the levels of blood platelet-activating-factors including prothrombin, sP-selectin and PAF acetylhydrolase.

b、Adhesion and morphology of blood cells

The blank PVC and Al_2O_3 -coated PVC (T-ALD and PE-ALD) samples are planned to be immersed in whole blood and incubated at 37°C for 1 hr under the static condition to check blood-surfaces adhesion. The samples are then washed gently with phosphate buffered saline (PBS), fixed with 2.5% glutaraldehyde solution for 2 hr at room temperature, and dehydrated in a gradient of ethanol/distilled water mixtures. Finally, the samples are undergone critical-point drying, and subsequently coated with gold ions and then inspected using a scanning electron microscopy.

c、Inflammatory response

After 1 hr immersion in whole blood, the inflammatory responses induced by blank PVC or surface-modified PVC samples are determined. The blood cells are collected, washed, and incubated with CD4/CD8, CD42b, CD45, or CD61/CD62P antibodies for 15 minutes on ice, and sorted using a fluorescence-activated cell sorter to evaluate the inflammatory responses.

IV. Projected Timeline

VIII. Anticipated Outcomes

A. Clinical improvement

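### Does the heading of assay c, the inflammatory response, promise more than its antibody panel can measure?

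*Protocol*

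**What the plan says.** Section III.C.3 of the Protocol lists three in vitro assays on fresh blood from healthy volunteers. Assay c compares blank with surface-modified PVC after one hour in whole blood. The cells are "incubated with CD4/CD8, CD42b, CD45, or CD61/CD62P antibodies for 15 minutes on ice" and then "sorted using a fluorescence-activated cell sorter to evaluate the inflammatory responses". The section does not say what each marker stands for, which readout is taken, or which direction counts as a lower response.

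Assay a, in the same section, measures "levels of blood platelet-activating-factors including prothrombin, sP-selectin and PAF acetylhydrolase". Section III.C.2 adds "Basic biological evaluations following ISO 10993/EN 30993 including chemical, mechanical, thermal and aging testing".

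The background sets out how the protocol understands inflammation. Section I.A.2 describes an "inflammatory response including coagulation, complement, cytokines and eicosanoid systems with crosstalk among them" and goes on to platelet adhesion and activation. Section I.B holds that "blood-surface interaction is a crucial promoter of the subsequent inflammation leading to coagulopathy". Section I.B.1 says that heparin-bonded circuits "have been reported to reduce blood cell trauma [12], complement [13] and granulocyte [14] activation". Section I.B.2 describes anti-platelet agents as "preventing platelets aggregation and possibly reducing inflammation". Among the anticipated outcomes, section VIII.A(2) forecasts a milder inflammatory reaction in patients as one reason for lower morbidity and mortality.

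**The concern.** A reader who knows these markers would see a platelet and leukocyte panel and not an inflammation panel. On standard roles, CD4, CD8 and CD45 identify leukocytes, CD42b and CD61 identify platelets, and CD62P shows platelet activation. Assay a places sP-selectin, the soluble form of CD62P on the same assumption, under platelet-activating factors. The same molecule therefore seems to count as platelet activation in one assay and as inflammation in another.

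Inflammation also has its own place in the protocol's argument. Section I.B treats it as a step on the way to coagulopathy, and section VIII.A(2) gives it as a benefit in addition to avoiding coagulopathy. Assay c is the only listed assay that carries inflammation in its heading. A difference between blank and coated PVC in CD62P or in cell proportions could be filed as an inflammatory result and then cited for a claim it cannot carry alone. At stake is how a laboratory result is interpreted. The result itself would not change.

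**Working it through.** The protocol gives no figure on this point to reproduce, so the check compares the passages.

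1. **What assay c lists.** Six antibodies: CD4, CD8, CD42b, CD45, CD61 and CD62P. On the assumed roles, three identify leukocytes, two identify platelets and one marks platelet activation (3 + 2 + 1 = 6).

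2. **What the protocol counts as inflammation.** Section I.A.2 names four systems: coagulation, complement, cytokines and eicosanoids. Assay c reads 0 of the 4 directly. Across assays a to c, prothrombin in assay a touches coagulation if it is taken as a coagulation protein (also an assumption). That gives 1 of 4, with complement, cytokines and eicosanoids unmeasured. The heading of assay c is therefore broader than its panel.

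3. **Whether the heading contradicts the protocol's own usage.** It does not. The list in I.A.2 is open, since it says what the response includes. It contains coagulation, and the same paragraph continues with platelet activation. Section I.B.2 ties platelet aggregation to inflammation. In that wide sense, a platelet-activation and leukocyte panel can sit under the heading as a partial, indirect measure.

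4. **Whether assay a fixes a stricter classification.** Its heading also covers prothrombin and PAF acetylhydrolase. It is a loose label and gives little ground for saying that the protocol excludes P-selectin from inflammation.

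5. **Whether any conclusion rests on assay c alone.** None does in the text. Section VIII.A(2) is a forecast about patients and does not cite the assay. Section I.C reasons about biocompatible materials in general. Section II leaves safety and effectiveness to in vitro and in vivo studies together. The in vivo work and the full content of the ISO 10993 evaluations cannot be seen here.

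6. **What a change would gain.** A new heading alters no data. Reading CD62P within CD61-positive events is already suggested by the written pair CD61/CD62P. The only change to laboratory practice would be to stain CD45 together with CD42b or CD61 so as to look for platelet-leukocyte aggregates. The protocol does not say whether the antibodies share a tube, so co-staining may already be intended. It would also add no complement, cytokine or eicosanoid measure, so the gap in step 2 would remain.

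**The case for a change.** The strongest case for a change is that the heading and stated purpose are fixed in the protocol. A later analysis plan could define gates and directions, but it could not add unmeasured systems to the panel. The background itself names complement and granulocyte activation when it describes heparin-bonded circuits, so the investigators had more direct measures of inflammation in view. Relabelling is almost free and would remove an invitation to over-read the result.

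Part of this stands. The heading is broader than the panel, and assay c alone does not support a general statement that the coating lowers inflammation.

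The rest does not carry a change. The protocol's wide use of the term makes the heading loose, but not wrong. The over-reading is a possible later misuse and appears nowhere in the text. Tube layout, gating and choice of readout are details that a protocol may leave to laboratory procedures or to the SAP, which is not at hand.

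**Conclusion.** No change to the plan is needed. The heading of assay c is wider than its panel but consistent with the protocol's own use of the term. The section shows no endpoint, sample size, patient decision or stated figure that depends on it. A new label would change no data, and different antibody pairing would not supply the missing measures.

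What remains is a caution for reporting. Results of assay c are best described as platelet activation and leukocyte/platelet phenotype, and should not serve alone as evidence of a generally lower inflammatory response.

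This rests on the standard roles of the six markers and of prothrombin, which the protocol does not state, and only on the three assays listed in III.C.3.
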